2. RATIONALE

As outlined above, HF is a significant problem in type 1 diabetes, with an estimated prevalence of 3-5%. Outcomes for individuals with type 1 diabetes and HF are worse than in those with type 2 diabetes or without diabetes, with increased mortality and hospitalisation rates. Critically, patients with type 1 diabetes have been excluded from pivotal trials of the latest advance in HF treatment (SGLT2i), potentially exacerbating these outcome disparities further.

The proposed trial will be the first to provide data on the efficacy and safety of sotagliflozin, in patients with type 1 diabetes and HF (regardless of LVEF). If a beneficial signal is found, this would provide strong support for extending the use of sotagliflozin in this group of patients with type 1 diabetes and adoption into clinical guidelines. A multi-centre, double-blind, randomised controlled trial to provide the strongest level of evidence for previous findings of the researchers will be conducted. Importantly, by choosing QoL measured using the KCCQ as the primary endpoint, an outcome that not only correlates strongly with mortality and hospitalisation but is also accepted by the US Food and Drug Administration as a valid endpoint for regulatory approval has been selected. The KCCQ is a 23-item self-administered questionnaire that measures the patient's perception of their health status, including HF symptoms, impact on physical and social function, and how their HF impacts their QOL within the preceding 2 weeks²⁹. Improvements in KCCQ score map very well to reductions in mortality and hospitalisation and SGLT2i have consistently improved KCCQ scores (Table 2). A 5-point increase in KCCQ score is traditionally considered clinically meaningful and is associated with a 7% reduction in mortality and HF hospitalisation³⁰. Given the prohibitive size of trial that would be required to demonstrate an improvement in mortality or HF hospitalizations with sotagliflozin in type 1 diabetes, the KCCQ represents an ideal endpoint for the trial. The proposed trial has the potential to be a high-impact, practice-changing trial.

Table 2. Summary of SGLT2i vs. placebo randomised trials in HF patients with QoL measured by KCCQ as the primary endpoint.

Trial	Intervention	Number of Participants	Diabetes Status	LVEF	KCCQ improvement at 3 months (SD)
DEFINE-HF³¹	Dapagliflozin	263	Type 2 diabetes or no diabetes	<40%	4.7

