3.2. Table of endpoints/outcomes

Primary Objective		
Objectives	Outcome Measures	Timepoint(s)
To investigate the effect of sotagliflozin 200mg once daily in addition to standard of care on quality of life	Change from baseline in KCCQ clinical summary score	Weeks 0 and 16

Secondary Objectives		
Objectives	Outcome Measures	Timepoint(s)
To investigate the effect of sotagliflozin 200mg once daily in addition to standard of care on QoL	Change from baseline in KCCQ clinical summary score	Weeks 0 and 4
	Change from baseline in KCCQ overall summary score	Weeks 0, 4 and 16
	Proportion of participants with a ≥ 5 , ≥ 10 and ≥ 15 point increase in KCCQ clinical and overall summary scores	Weeks 0 and 16
	Change from baseline in Diabetes Treatment Satisfaction Questionnaire (DTSQs and DTSQc)	Weeks 0 and 16
	Change from baseline in EQ-5D-5L score	Weeks 0 and 16
To investigate the effect of sotagliflozin 200mg once daily in addition to standard of care on walking distance	Change from baseline in distance covered during 6-minute walk test	Weeks 0 and 16
To investigate the effect of sotagliflozin 200mg once daily in addition to standard of care on NT-proBNP	Change from baseline in NT-proBNP	Weeks 0 and 16
To investigate the effect of sotagliflozin 200mg once daily in addition to standard of care on glycaemic control	Change from screening in HbA1c	Screening and week 16

To provide information on safety and tolerability of sotagliflozin 200mg once daily in addition to standard of care compared to placebo	Proportion of participants with level 2 or level 3 hypoglycaemia	Week 0 to weeks 16 and 20
	Proportion of participants with DKA	Week 0 to weeks 16 and 20
	Proportion of participants requiring hospitalisation due to HF	

Exploratory Objectives		
Objectives	Outcome Measures	Timepoint(s)
To investigate the effect of sotagliflozin 200mg once daily in addition to standard of care on HF symptoms, signs and clinical outcomes	Change from screening in New York Heart Association (NYHA) class	Screening, weeks 16 and 20
	Change from baseline in daily loop diuretic dose	Weeks 0 and 16
	Change from baseline in systolic and diastolic blood pressure.	Weeks 0 and 16
	Number of hospitalizations and deaths (first and total number) due to heart failure	Week 0 to weeks 16 and 20
To investigate the effect of sotagliflozin 200mg once daily in addition to standard of care on renal parameters	Change from baseline in eGFR, serum creatinine, urine albumin to creatinine ratio	Weeks 0 and 16

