6.2. For randomisation

6.2.1. Inclusion criteria

1. Age 18 years to <85 years.
2. Type 1 diabetes.
3. Insulin dose ≥ 0.5 units/kg body weight at screening **or** BMI ≥ 25 kg/m² at screening
4. Using continuous glucose monitor at screening or willing to use one for the duration of the trial.
5. Diagnosis of heart failure (HF) or high-risk for HF, defined as any of the following:
 - NT-proBNP ≥ 250 ng/L for those in atrial fibrillation/flutter, ≥ 125 ng/L for those in all other rhythms

or

Previous HF hospitalisation where HF was documented as the primary cause of hospitalisation and there was a requirement for loop diuretics

or

Impaired left ventricular (LV) function (i.e. LVEF <50% by any imaging modality) at any time

or

Preserved LV systolic function (LVEF $\geq 50\%$) with left atrial enlargement (2-dimensional measurement of left atrial width ≥ 3.8 cm or left atrial length ≥ 5.0 cm or left atrial area ≥ 20 cm² or left atrial volume index > 29 ml/m²) within the last 24 months.

or

Preserved LV systolic function (LVEF $\geq 50\%$) with left ventricular hypertrophy (2-dimensional measurement of end-diastolic interventricular septal diameter ≥ 1.2 cm or end-diastolic left ventricular posterior wall diameter ≥ 1.2 cm) within the last 24 months.

or

Preserved LV systolic function (LVEF $\geq 50\%$) with diastolic dysfunction (septal e' <7 cm/sec or lateral e' <10 cm/sec or average E/e' ≥ 15) within the last 24 months.

6. New York Heart Association Class II-IV at screening.
7. Kansas City Cardiomyopathy clinical summary score <85 at screening.

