7.6. Baseline data

Baseline data will be collected at day 0 as per Schedule of Procedures, Appendix 4, and as described below, section 7.7.

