10. STATISTICS AND DATA ANALYSIS

10.1. Sample size calculation

The sample size calculation was informed by the recent DEFINE-HF³¹ trial of dapagliflozin vs. placebo in participants with symptomatic HF with reduced ejection fraction and type 2 diabetes or no diabetes, in which dapagliflozin caused an improvement of 4.7 points in the KCCQ Clinical Summary Score (SD 13.7) compared to placebo. To achieve 80% power to identify this difference at an alpha of 0.05, 268 participants (134/group) are required. Accepting the potentially greater attrition in a type 1 diabetes population a ~15% trial dropout will be allowed for and therefore it is planned to recruit 320 individuals. An improvement of ~5 points in KCCQ is accepted as a clinically important difference²⁹ and is certainly consistent with that seen in SGLT2i HF trials (Table 2), for example PRESERVED-HF³², in which individuals with HFpEF were recruited and the magnitude of improvement in KCCQ was even larger than in DEFINE-HF (5.8 points). The KCCQ Clinical Summary Score is accepted for use in regulatory submissions to the FDA.

CMR sub-study sample size calculation

A recent study found that dapagliflozin caused a 50% increase in myocardial flow reserve measured using PET/CT.⁴⁴ In a predominantly non-diabetic cohort a 1SD increase in stress MBF (0.71 mL/g/min) was associated with a 54% relative risk reduction in MACE after a median of 20 months⁴⁷, while CMR-derived MPR is ~20% lower in T1D than in controls⁴⁸, so it is hypothesised that changes of these magnitudes in stress MBF and/or MPR could be clinically meaningful. To have 90% power to detect a 0.71 mL/g/min in stress MBF between sotagliflozin and placebo groups 44 participants are required, assuming balance in randomisation (22 per group).

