10.3.1. Primary outcome analysis

The primary endpoint of change in KCCQ clinical summary score at 16 weeks will be analysed using mixed effect models adjusting for baseline KCCQ, age, eGFR and LVEF.

Statistical significance will be defined as a two-sided p value <0.05 for all tests.

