16.4. Appendix 4 – Schedule of Procedures

	Visit 1 (Screening)	Visit 2	Visit 3 (Baseline)	Visit 4	Visit 5	Visit 6	Visit 7	Visit 8
	-30 days to -14 days	-7 days +/- 3 days	Day 0	Week 1 +/- 3 days	Week 4 +/- 3 days	Week 10 +/- 3 days	Week 16 +/- 3 days	Week 20 +/-3 days
	Research Site	Remote/ Research Site	Research Site	Remote/ Research Site	Research Site	Remote/ Research Site	Research Site	Remote/ Research Site
Informed Consent	X							
Eligibility	X		X					
Demographics	X							
Medical History	X							
NYHA Class	X						X	X
Record Concomitant Medications	X	X	X	X	X	X	X	X
Adverse Events		X	X	X	X	X	X	X
Weight	X		X				X	
Height, Waist and hip circumference	X							
Blood Pressure & pulse	X		X				X	
Physical Examination	X						X	
ECG	X							
Echocardiography, if required		X						
Review of Glucose Management including ketone check		X	X	X	X	X	X	X
Education for glucose and ketone management		X	X	X	X	X	X	X
Registration with app such as LibreView/Clarity etc. (if not already signed up), optional		X						
Documentation of summary Data and/or glucose readings from CGM, from previous 2 weeks			X		X		X	
Documentation of glucose and ketone readings		X	X	X	X	X	X	X
Documentation of hypoglycaemic and DKA events		X	X	X	X	X	X	X

	Visit 1 (Screening)	Visit 2	Visit 3 (Baseline)	Visit 4	Visit 5	Visit 6	Visit 7	Visit 8
	-30 days to -14 days	-7 days +/- 3 days	Day 0	Week 1 +/- 3 days	Week 4 +/- 3 days	Week 10 +/- 3 days	Week 16 +/- 3 days	Week 20 +/-3 days
	Research Site	Remote/ Research Site	Research Site	Remote/ Research Site	Research Site	Remote/ Research Site	Research Site	Remote/ Research Site
KCCQ	X		X		X		X	
DTSQ (status at baseline, change and status at 16 weeks)			X				X	
EQ-5D-5L			X				X	
6 minute-walk test			X				X	
Urine pregnancy test	X		X					
Safety Bloods (FBC, U&E, LFT, glucose)	X		X		X		X	
HbA1c	X						X	
NT-proBNP or BNP (local) if required	X							
NTproBNP for central lab analysis (Dundee)			X				X	
C-peptide for central lab analysis (Dundee)			X					
Urine albumin, creatinine, sodium			X		X		X	
Additional research bloods			X				X	
Additional research urine samples			X				X	
Randomisation			X					
Dispensing of IMP*			X					
Compliance to IMP				X	X	X	X	
IMP Accountability			X				X	

	Visit 1 (Screening)	Visit 2	Visit 3 (Baseline)	Visit 4	Visit 5	Visit 6	Visit 7	Visit 8
	-30 days to -14 days	-7 days +/- 3 days	Day 0	Week 1 +/- 3 days	Week 4 +/- 3 days	Week 10 +/- 3 days	Week 16 +/- 3 days	Week 20 +/-3 days

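### Adding the screening KCCQ clinical summary score to the primary model, beside the Day 0 score, would be a nearly free and possibly small gain in precision

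*Protocol*

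**What the plan says.** Section 10.3.1 fixes the covariates of the primary model: the endpoint "will be analysed using mixed effect models adjusting for baseline KCCQ, age, eGFR and LVEF". Section 7.6 defines baseline: "Baseline data will be collected at day 0 as per Schedule of Procedures, Appendix 4". Section 3.2 gives the primary outcome as "Change from baseline in KCCQ clinical summary score", at weeks 0 and 16.

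The same score is also measured earlier. Inclusion criterion 7 in section 6.2.1 requires a "Kansas City Cardiomyopathy clinical summary score <85 at screening". The schedule in Appendix 4 marks the KCCQ at Visits 1, 3, 5 and 7, with Visit 1 falling 30 to 14 days before Day 0. Every eligible randomised participant therefore has two pre-randomisation values of the primary-endpoint score, and the primary model names one of them.

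**The concern.** A single KCCQ reading is a noisy measure of a person's usual level. Section 2 says the questionnaire covers "how their HF impacts their QOL within the preceding 2 weeks", and the two visits are at least 14 days apart, so the recall periods at most touch. The screening score may therefore explain week-16 variation that the Day 0 score leaves unexplained. Because it is fixed before randomisation, adjusting for it cannot bias the treatment comparison. It is already collected and should be nearly complete.

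What is at stake is the width of the confidence interval for the primary effect, in a trial planned at 80% power. The validity of the result is not in question. The point belongs here because section 10.3.1 names its covariates; an analysis plan that follows the list would leave the screening score out.

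**Working it through.** **The plan's own figure.** Section 10.1 states that "dapagliflozin caused an improvement of 4.7 points in the KCCQ Clinical Summary Score (SD 13.7) compared to placebo", and that "To achieve 80% power to identify this difference at an alpha of 0.05, 268 participants (134/group) are required". With a two-sided alpha of 0.05:

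n per arm = 2 × (1.960 + 0.842)² × (13.7 / 4.7)² = 2 × 7.85 × 8.50 ≈ 133.4, rounded up to 134, or 268 in total.

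This reproduces. With 320 randomised and 15% dropout, 320 × 0.85 = 272 are evaluable, or 136 per arm, with power 80.8%.

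**Formula for the gain.** Let S be the screening score, B the Day 0 score and Y the week-16 score. The residual variance of Y given both S and B, relative to that given B alone, is

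k = 1 − (r_SY − r_SB × r_BY)² / [(1 − r_SB²)(1 − r_BY²)].

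If all three correlations equal r, this becomes (1 + 2r) / (1 + r)². The covariates age, eGFR and LVEF and the week-4 KCCQ are left out of this calculation.

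**Assumed inputs.** The protocol gives none of these correlations, so all are assumptions. The power column treats 13.7 as the residual SD of the current model and uses SD 13.7 × √k with 136 per arm.

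| r_SB | r_BY | r_SY | k | Variance cut | Power |
|---|---|---|---|---|---|
| 0.80 | 0.70 | 0.56 | 1.000 | 0% | 80.8% |
| 0.90 | 0.70 | 0.65 | 0.996 | 0.4% | 80.9% |
| 0.80 | 0.70 | 0.60 | 0.991 | 0.9% | 81.1% |
| 0.85 | 0.70 | 0.65 | 0.979 | 2.1% | 81.6% |
| 0.80 | 0.70 | 0.65 | 0.956 | 4.4% | 82.5% |
| 0.80 | 0.70 | 0.70 | 0.893 | 10.7% | 84.9% |
| 0.60 | 0.60 | 0.60 | 0.859 | 14.1% | 86.3% |
| 0.70 | 0.70 | 0.70 | 0.830 | 17.0% | 87.4% |
| 0.80 | 0.80 | 0.80 | 0.802 | 19.8% | 88.5% |

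Worked example, fifth row: (0.65 − 0.80 × 0.70)² = 0.0081; (1 − 0.64)(1 − 0.49) = 0.1836; 0.0081 / 0.1836 = 0.044; k = 0.956.

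The first row is the case where screening adds nothing once Day 0 is known (0.80 × 0.70 = 0.56).

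**Truncation at 85.** Criterion 7 cuts off high screening scores, which trims the gain. Simulated with that cut and a scale bounded at 0 and 100, the equal-correlation ratios become 0.890, 0.861 and 0.829 for r = 0.6, 0.7 and 0.8. These are cuts of 11%, 14% and 17%, and power of about 85%, 86% and 87%. A second simulation, unbounded, with an assumed mean of 60 or 70 and SD 20, gives 0.857 and 0.874 at r = 0.7. In that simulation the 0.80/0.70/0.70 row gives a cut of about 8–10%.

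**The other reading of SD 13.7.** Section 10.1 does not say which SD this is. If it is the SD of change, with equal variances at the two visits, the Day 0-adjusted residual variance is 13.7² × (1 + r)/2. For r = 0.5 to 0.8 the residual SD is 11.9 to 13.0, and the current model already has about 90% to 85% power at 136 per arm.

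**Cost.** One degree of freedom out of about 270 inflates variance by about 1/270 = 0.4% at worst.

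**The case against.** The planned analysis contains no mistake. Adjusting for the Day 0 value of the outcome is standard and valid, and the sample size is right for its inputs. Section 10.3 also leaves detail on primary and adjusted analyses to a statistical analysis plan that is not at hand. The first part stands in full. The second stands only in part, because section 10.3.1 already lists its covariates without the screening score.

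The large gains need equal correlations across unequal gaps. Screening and Day 0 are 14 to 30 days apart; Day 0 and week 16 are 112 days apart. Scores closer in time would normally correlate more strongly, which pushes the gain towards the upper rows of the table. This objection stands and limits the claim.

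A reader might infer from the two-week recall that the two scores are close to independent readings of one stable baseline. Separate recall periods show only that different fortnights are covered. Deviations from a person's usual level can persist or drift, and if Day 0 supersedes screening the gain is zero. A reader might also infer that the trial is certain to lose precision or is short of power. The documents support neither: the correlations are not given, and the power figure depends on what SD 13.7 represents.

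**Conclusion.** The primary model omits a second pre-randomisation value of its own endpoint score that every eligible randomised participant has. Including it would be unbiased and almost costless, and is worth considering. The size is uncertain. The variance cut is roughly 0–5% when screening and Day 0 are closely correlated and screening predicts week 16 less well than Day 0 does. It is about 11–17%, after truncation, when all three correlate equally at 0.6–0.8, with intermediate patterns between. Power at 136 per arm goes from about 81% to between 81% and about 86–87% if 13.7 is a residual SD; if it is the SD of change, power already exceeds 80% without the extra term. The facts about the model and the data are firm; the amount gained is an assumption. This is an optional improvement to a valid plan.

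**What to change.** In section 10.3.1, list the KCCQ clinical summary score at Visit 1 and at Visit 3 as two covariates, together with age, eGFR and LVEF. Keep change from Visit 3 as the outcome. Use separate terms rather than their mean, because eligibility truncates the screening score at 85 but not the Day 0 score. Treat the KCCQ overall summary score in the same way for that secondary outcome.

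Pre-specify this before unblinding. Section 10.3 allows the analysis plan to be finalised up to data lock, and section 7.4 places end-of-trial unblinding after data lock, so the change can be made blind. It needs no extra participants, visits or questionnaires.

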10.3. Statistical analysis plan

Statistical support will be provided by the TCTU trial statistician.

A statistical analysis plan will be developed prior to participant recruitment and will be finalised prior to data lock. Any deviations from this will be described and justified in the final report.

The statistical analysis plan will detail the summary of baseline data and flow of participants, primary and secondary outcome analysis, subgroup analyses, adjusted analysis, participant population and, procedure(s) to account for missing or spurious data.

Baseline demographic and clinical data will be described between sotagliflozin and placebo arms as mean +/- SD for continuous variables and number and percentage for categorical variables. Differences between arms will be compared using t-tests or chi-square tests as appropriate.

CMR sub-study statistical analysis

The CMR scans may be analysed during the course of the main trial, however, as unblinding will not occur until database lock for the main trial, the primary outcome of the sub-study will only be assessed at the same time as the main trial results are available. The primary analysis will be performed using mixed effects models on the intention-to-treat dataset adjusting for relevant variables. Changes in sub-study outcomes will also be compared to the main trial outcomes including change in KCCQ score and NT-proBNP.

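### Section 10.3.1 calls any two-sided p<0.05 statistically significant, so the rule covers about 20 secondary and 34 exploratory comparisons without family-wise control; section 10.3 adds significance tests of randomised baseline data

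*Protocol*

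**What the plan says.** Section 10.3.1 describes one primary analysis, at one time point: "The primary endpoint of change in KCCQ clinical summary score at 16 weeks will be analysed using mixed effect models", with adjustment for baseline KCCQ, age, eGFR and LVEF. The sentence after it reads "Statistical significance will be defined as a two-sided p value <0.05 for all tests". This is the protocol's only definition of significance. No section orders the secondary outcomes, divides alpha among them, or says that their p values are descriptive.

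Section 3.2 has 11 secondary rows and 14 exploratory rows. Many rows hold several comparisons. "Change from baseline in KCCQ overall summary score" is due at weeks 4 and 16. The responder row applies thresholds of 5, 10 and 15 to a "point increase in KCCQ clinical and overall summary scores", which makes six proportions.

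Section 10.3, after saying that baseline data will be summarised by arm, adds "Differences between arms will be compared using t-tests or chi-square tests as appropriate". It leaves the detail of primary and secondary outcome analysis to the SAP.

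Section 2 says of a beneficial signal that "this would provide strong support for extending the use of sotagliflozin in this group of patients".

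**The concern.** The SAP is not at hand, and a protocol may leave multiplicity to it. The point here is what the protocol itself fixes. Read as written, any single secondary or exploratory p value under 0.05 is a statistically significant result, with the same standing as the primary test. With dozens of comparisons, an isolated one of that kind is to be expected by chance alone. It would be most misleading if the primary result were null and a secondary one were put forward in its place.

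The baseline sentence is a separate and smaller fault. Under randomisation the null hypothesis of a baseline comparison is true by design. A significant result says nothing about the population and may be misread as a failure of randomisation.

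**Working it through.** **The plan's own figure first.** Section 10.1 gives a difference of 4.7, SD 13.7, 80% power and alpha 0.05.

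n per group = 2 × (1.960 + 0.842)² × 13.7² / 4.7² = 133.4, so 134 per group and 268 in all, as stated (power 80.2%). With 15% dropout, 268 / 0.85 = 315.3, so 316, against 320 planned. The design is a single test at 0.05, and the figure reproduces.

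**Counting comparisons (section 3.2).** Each score, threshold and post-baseline time point counts as one.

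| Secondary outcome | Comparisons |
|---|---|
| KCCQ clinical summary score, week 4 | 1 |
| KCCQ overall summary score, weeks 4 and 16 | 2 |
| KCCQ responders, 3 thresholds × 2 scores | 6 |
| DTSQ status and change | 2 |
| EQ-5D-5L, 6-minute walk, NT-proBNP, HbA1c | 4 |
| Hypoglycaemia and DKA, to weeks 16 and 20 | 4 |
| Heart failure hospitalisation | 1 |
| **Total** | **20** (15 efficacy, 5 safety) |

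Exploratory: NYHA 2, loop diuretic 1, blood pressure 2, heart failure hospitalisations and deaths 4, renal 3, insulin doses 6, weight 1, CGM metrics 14, ketosis 1, total 34. The C-peptide associations and the CMR sub-study outcomes are not counted.

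**Chance of at least one p<0.05 when none of the k effects is real, independent tests:** 1 − 0.95^k. The expected number of false positives is 0.05 × k, whatever the correlation.

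- k = 15 (secondary efficacy only): 1 − 0.95^15 = 54%; expected 0.75
- k = 20 (all secondary): 1 − 0.95^20 = 64%; expected 1.0
- k = 34 (exploratory): 1 − 0.95^34 = 83%; expected 1.7

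**Allowing for correlation.** The protocol gives no correlations, so a range is assumed. The model is equicorrelated normal statistics, Z = √r × F + √(1 − r) × E, with 200,000 runs and a count of |Z| > 1.96. For k = 20:

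| Assumed r | At least one p<0.05 | Mean number |
|---|---|---|
| 0 | 64% | 1.0 |
| 0.3 | 54% | 1.0 |
| 0.5 | 42% | 1.0 |
| 0.7 | 29% | 1.0 |

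Correlation makes the false positives cluster; it does not reduce their average number. Even at r = 0.7 the rate is about six times 5% (0.29 / 0.05 = 5.8).

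**Baseline tests.** The protocol does not say how many variables will be tested. With m variables the expected number of chance flags is 0.05 × m. For an assumed m of 10 to 30 that is 0.5 to 1.5, and somewhat less where a variable is also a stratification factor (section 7.3).

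**The case against.** **Scope.** The sentence stands under the primary outcome heading, and could mean only the primary endpoint in its intention-to-treat, modified intention-to-treat and per-protocol versions (section 10.5). No section says that every cell of the tables will be tested. The ambiguity is real, but the wording is general and no other rule exists for the remaining outcomes.

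**A SAP hierarchy could sit beside it.** Each step of a fixed sequence is also tested at 0.05. This stands in part: the level is compatible. A sequence, however, withholds significance from later tests after a failed step, and the sentence as written grants it to any test below 0.05.

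**The figures depend on conventions.** The 20 comparisons are an expansion of 11 rows. Nine of the 15 efficacy comparisons come from the KCCQ and overlap heavily. Adjustment is not usual for the five safety proportions. All of this stands.

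**Stronger readings that the document does not support.**

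- A reader might infer that a false secondary finding is more likely than not. That holds at independence or low correlation, but not at r = 0.5 (42%) or 0.7 (29%).
- A reader might pool all 54 comparisons (20 + 34) under a global null, giving 1 − 0.95^54 = 94%. The background in section 1 expects real effects on HbA1c, weight, insulin dose and time in range. Insulin dose, weight and CGM metrics supply 6 + 1 + 14 = 21 of the 34 exploratory comparisons, so many significant results there could be true.
- A reader might say that there is no error control at all. Each test is still held at 5%; what is absent is control across the family.
- A reader might fear that baseline p values will steer the adjustment. The main model's covariates are named in section 10.3.1. The CMR analysis leaves its covariates open, but nothing says that they will be chosen by baseline tests.
- Section 2's statements on guidelines and regulatory acceptance concern a beneficial signal and the KCCQ as primary endpoint. They are not claims about secondary outcomes.

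**Conclusion.** The point holds as a fault in two stated rules. The significance sentence gives any single secondary or exploratory p<0.05 the label of statistical significance. If the 20 secondary comparisons all had no true effect, the chance of at least one such label would be about 29% to 54% at assumed correlations of 0.7 to 0.3 (64% at independence), with 1.0 expected. This rests on the count of 20, on the no-effect condition, which is doubtful for HbA1c in particular, and on correlations that the protocol does not supply. The baseline tests are uninformative by design, whatever their number.

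The primary conclusion, its 0.05 level and the sample size of 268 evaluable (320 recruited) are untouched. It is a worthwhile correction to what the trial may claim, and no threat to its main result.

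**What to change.** In section 10.3.1, limit the significance claim to the primary endpoint. Suggested text: the primary endpoint will be tested at two-sided 0.05; all other outcomes will be reported as estimates with 95% confidence intervals and nominal p values, without a claim of statistical significance. If the investigators want formal claims for a few secondary outcomes, such as 6-minute walk distance or NT-proBNP, they can name a fixed sequence after the primary, each step at 0.05 and stopping at the first failure. Either route leaves the sample size unchanged. A Bonferroni split over 20 comparisons would mean 0.05 / 20 = 0.0025 each. At that level a difference of 4.7 with SD 13.7 and 134 per group has only 41% power, so it is the less attractive choice.

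In section 10.3, delete the sentence on t-tests and chi-square tests, so that baseline data are only described by arm.

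The cost is an amendment of wording, with the SAP aligned to it. Data collection and conduct do not change. The downside is that secondary outcomes outside any stated sequence can carry no formal significance claim.
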